## **3.2 General Definitions**

### **3.2.1 Study Day**

Study Day 0 is defined as the day of randomization.

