### 3.2.2 Treatment Period

Participants will be engaged in a 180-day (6 month) treatment period of active intervention (PILOT) or TAU. Treatment period visits are scheduled for Day 30, Day 90, and Day 180. The study visit windows are inclusive and listed in Table 2.

Table 2: Study Visit Windows		
Study Visit	Visit Window	
Baseline	-	Day 7
Day 30	Day 23	Day 51
Day 90	Day 76	Day 104
Day 180	Day 159	Day 194

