##### 7.4.1 Steps Achieved on Modified SUD Cascade of Care

At Day 30, Day 90, Day 180, and Day 210 visits, participants will be asked to complete an assessment battery to assess steps achieved on the modified SUD Cascade of Care. This battery includes the Harm Reduction Checklist (HRC form), Steps Achieved Assessment (SAA form), MOUD Confirmation Assessment (MCA form), DSM-5 Checklist for Substance Use (DSM form), Urine Drug Test (UDT form), and the Assessment of Recovery Capital Scale (ARC form).

CASCADE	OD Identification & Harm Reduction	Engagement in Care		MOUD Initiation	MOUD Retention			Treatment Response & Remission (6 month)		
STEPS	1 ↑ Harm Reduction	2 Any Care	3 Regular Care	4 Any MOUD	5 MOUD X 1 mo	6 MOUD X 3 mo	7 MOUD X 6 mo	8 ↓ SUD Severity	9 Early Remission	10 ↑ Recovery Score
MEASURE	HRC	SAA		SAA	SAA and MCA			DSM and UDT	ARC	

Step Eligibility: All enrolled participants will be considered to have 0 steps achieved at the time of study entry (baseline). A participant will be counted as having met a particular step if criteria are met at ANY study visit or for any length of time during the study, even if the participant subsequently does not endorse a previously endorsed item. Achievement of these steps is not necessarily sequential nor contingent upon previous steps. If data is missing for any step, it will be considered not met. That is, either evidence was previously obtained that a step was achieved, or evidence was never collected that the step was achieved.

The following will count as attaining a step:

1. Increase in Harm Reduction Exposure and Behaviors: A participant will have attained Step 1 if, on the HRC form: (1) any unchecked “achieved” box becomes checked, (2)

total score of checked boxes increases from baseline at any time during study (even if score subsequently decreases), or (3) if the Narcan availability item is checked as “Often” or “Very Often” at baseline *and* remains checked at any other study visit OR becomes checked as “Often” or “Very Often” at any visit subsequent to baseline. This assessment can be completed in person, electronically, or over the phone. A participant will be counted as having met Step 1 if the above criteria are met at ANY study visit, even if the participant subsequently does not meet the step criteria or does not endorse a previously endorsed item.

Item	Variable
Have you been provided information about safer injection practices and/or needle exchange programs?	HRSAFEIP

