3. **Engagement in care – Regular:** A participant will have attained Step 3 if the participant self-reports completion of any of the SAA form Step 2 b-d activities at least 3 times in the past 90 days (SA12SPS3, SAPEERS3, SAFMTRS3). A participant will be counted as having met Step 3 (after baseline assessment) if the above criteria are met for any length of time during the study, even if the participant subsequently does not meet the step criteria or does not endorse a previously endorsed item.

If data is collected multiple times for the same visit (i.e., a form is submitted for visit number M03 and supplemental visit M03S), the data from the supplemental visit will replace any missing values for Step 3 from the original visit. The step can be achieved using data from the original or supplemental visit form.

4. **Taking MOUD – Any:** A participant will have attained Step 4 (after baseline assessment) if they self-report taking any dose of MOUD on the SAA form (no confirmation needed, but self-report of at least one dose; SAMOUDM1, SAMOUDM3, SAMOUDM6). A participant will be counted as having met Step 4 if the above criteria are met at ANY non-baseline study visit, even if the participant subsequently does not endorse a previously endorsed item.
5. **Taking MOUD consistently over the past 30 days:** A participant will have attained Step 5 if they self-report taking MOUD at least 20 of the past 30 days (SAA.SAMODDM1) AND toxicology screen(s) are positive for buprenorphine or methadone (MCA. MCMOUDSR), consistent with self-report (MCA. MCMOUDY), as confirmed at study visits.

If (1) the participant self-reports taking naltrexone (SAA. SAVIV), or if (2) the toxicology screen(s) are negative (MCA. MCMOUDSR), unable to be obtained, or inconsistent with self-report (e.g., a participant did not take MOUD in past 10 days, but did take MOUD the previous 20 days; (MCA. MCMOUDY)), Step 5 can also be confirmed by either (a) confirmation with treatment provider (MCA. MCPRVDR) or pharmacy of prescription written and/or dispensed consistent with MOUD availability 20 of the past 30 days (MCA. MCPHARMA); OR (b) participant providing the prescription bottle at the study visit or video chat (utilizing HIPAA-compliant platform) of a prescription bottle including matching name, medication, and date dispensed consistent with MOUD availability 20 of

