the past 30 days prior to the study visit (can be provided up to 90 days after the scheduled study visit; MAC. MCPPTRX). A participant will be counted as having met Step 5 (after baseline assessment) if the above criteria are met for any length of time during the study, even if the participant subsequently does not endorse a previously endorsed item.

6. **Taking MOUD consistently over the past 90 days:** A participant will have attained Step 6 if the participant self-reports taking MOUD at least 70 of the past 90 days (SAA form) AND toxicology screen(s) are positive for buprenorphine or methadone (MCA form), consistent with self-report. If (1) the participant self-reports taking naltrexone, or if (2) the toxicology screen is negative, unable to be obtained, or inconsistent with self-report, this step can be confirmed by either (a) confirmation with treatment provider or pharmacy of prescription written and/or dispensed consistent with MOUD availability 70 of the past 90 days; OR (b) participant providing the prescription bottle at the study visit or a video chat (utilizing HIPAA-compliant platform) of the prescription bottle including name, medication, and date dispensed consistent with MOUD availability 70 of the past 90 days (can be provided up to 90 days after the scheduled study visit). A participant will be counted as having met Step 6 if the above criteria are met for any length of time during the study, even if the participant subsequently does not endorse a previously endorsed item.

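### At the Day 30 visit, Step 3 can be met wholly, and Step 6 only with a large contribution, from time before randomization, which dilutes the cascade comparison

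*SAP*

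**What the plan says.** Under SAP 7.4.1, Step 3 is met by self-reported recovery meetings, peer sessions or formal SUD treatment "at least 3 times in the past 90 days". Step 6 is met if the participant "self-reports taking MOUD at least 70 of the past 90 days", with toxicology, provider, pharmacy or prescription-bottle confirmation. Protocol 7.2.1 uses the same definitions.

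Other provisions decide what period these look-backs cover:

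- **Visits.** SAP 7.4.1: "At Day 30, Day 90, Day 180, and Day 210 visits, participants will be asked to complete an assessment battery".
- **Timing.** SAP 3.2.1: "Study Day 0 is defined as the day of randomization". SAP 3.2.2: "The study visit windows are inclusive and listed in Table 2". The windows are Day 23 to 51 for Day 30, Day 76 to 104 for Day 90, and Day 159 to 194 for Day 180.
- **Retention of credit.** A step counts "if criteria are met at ANY study visit or for any length of time during the study" and is not removed later.
- **Starting point.** SAP 7.4.1 assigns every participant zero steps at entry. Protocol 11.5.4 gives the baseline Step 2-7 form a descriptive role only, so earlier activity is not subtracted.

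Step 7 is reserved for participants who complete the Day 180 visit. Steps 3 and 6 carry no comparable limit. The step-count model in SAP 7.5.1 includes Day 30, and the per-step logistic models in SAP 7.8 are repeated for the 30-day outcomes.

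**The concern.** A 90-day recall taken about 30 days after randomization must reach back before it. The zero-at-entry rule presents the count as attainment during the study, yet part of what is counted at Day 30 happened earlier.

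Prior care is to be expected. Protocol 13.1 anticipates existing treatment relationships, including MOUD, and no eligibility criterion excludes people already in care. Under Protocol 10.1, screening follows ED stabilization and usual care, which may include a TAU peer. A peer session at the index visit can therefore precede randomization and supply one of the three Step 3 contacts.

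Credits of this kind are added to both arms. They pull the steps rate ratio and the Step 3 and Step 6 odds ratios toward 1, and so could hide part of a real PILOT effect.

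**Working it through.** The documents give no power, sample size or expected rate for this outcome, so there is no stated figure to reproduce.

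**Date arithmetic.** For a visit on Study Day d:

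- recalled days before randomization = max(0, 90 − d)
- fewest earlier MOUD days that Step 6 needs = max(0, 70 − d)
- fewest later MOUD days that Step 6 needs = 70 − max(0, 90 − d)

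| Visit day | Recalled days before Day 0 | Share of 90 | Step 6: earlier days needed | Step 6: later days needed |
|---|---|---|---|---|
| 23 | 67 | 74.4% | 47 | 3 |
| 30 | 60 | 66.7% | 40 | 10 |
| 45 | 45 | 50.0% | 25 | 25 |
| 51 | 39 | 43.3% | 19 | 31 |
| 76 | 14 | 15.6% | 0 | 56 |
| 90 | 0 | 0.0% | 0 | 70 |

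At an in-window Day 30 visit at most 51 days have passed since randomization, against 70 required. Every Step 6 credit at that visit therefore depends partly on earlier MOUD use. Step 3 needs only three contacts, and all three can fall in the 39 to 67 earlier days.

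**Dilution of Step 3 (all rates assumed).** Let q be the proportion of each arm that qualifies from earlier contacts and p the true post-randomization proportion. If the two are independent, the observed proportion is 1 − (1 − q)(1 − p). Take p = 30% in TAU and 45% in PILOT, a true ratio of 1.50:

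- q = 3%: 32.1% vs 46.65%, ratio 1.45
- q = 5%: 33.5% vs 47.75%, ratio 1.43
- q = 10%: 37.0% vs 50.5%, ratio 1.36
- q = 25%: 47.5% vs 58.75%, ratio 1.24

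With p = 40% vs 60% and q from 10% to 40%, the ratio falls from 1.50 to between 1.39 and 1.19. With 75 per arm, power for that single step falls from 69% to between 60% and 36%.

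**Effect on the ten-step count (all rates assumed).** Suppose the other nine steps sum to a mean of 3.0 in TAU and 3.6 in PILOT, with Step 3 at 30% vs 45%:

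- no earlier credit: (3.6 + 0.45) / (3.0 + 0.30) = 1.227
- q = 10%: (3.6 + 0.505) / (3.0 + 0.37) = 1.218
- q = 25%: (3.6 + 0.5875) / (3.0 + 0.475) = 1.205

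The count ratio moves by about 0.01 to 0.02 from Step 3 alone.

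**The case against.** **The form is not in the documents.** Protocol 11.5.4 says the Step 2-7 form is used at follow-up visits where applicable, and the only visit example in the Step 3 text appears to be a month-3 visit. The form may already hold the 90-day items back to Day 90. That possibility stands, but neither text states such a rule. The phrase in Step 3 that places credit after the baseline assessment limits the visit, not the period recalled, and Step 6 lacks even that phrase.

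**Step 6 is not purely past behavior.** A reader might infer that PILOT could have no influence on a Day 30 Step 6 credit. The documents do not support that: at Day 30 at least 10 of the 70 MOUD days must follow randomization (31 at Day 51), with confirmation as well. Someone who stays on MOUD and attends the Day 90 visit would earn Step 6 anyway. The Day 180 count is therefore affected mainly through people who stop MOUD or miss later visits after Day 30.

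**The cascade partly credits maintained status by design.** Step 1 accepts naloxone availability that was already frequent at baseline and remains so, and Steps 4 and 5 can credit people who continue MOUD. This is fair as far as it goes. It does not cover Step 3 at Day 30, which can be met with no contact at all after randomization.

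**Randomization balances prior care.** A reader might infer bias in favor of one arm, and that would be wrong. Prior care is balanced in expectation, so false-positive results are not the issue. Equal credit added to both arms still dilutes a real difference. The balance argument in SAP 7.5.1 concerns baseline OUD and SUD status, not the look-back.

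**The prior-care rates are guesses.** This stands. The nearest figure, 11% SUD treatment engagement one month after overdose (Protocol 4.2), covers a different period and a narrower set of activities.

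**Conclusion.** The point holds for the plan as written. A Day 30 visit can credit Step 3 from contacts made entirely before randomization. It can credit Step 6 only if at least 40 of the 70 MOUD days came before randomization (47 at Day 23, 19 at Day 51). These credits persist to Day 180 and enter the Day 30 per-step models, which conflicts with the zero-at-entry premise.

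The consequence is non-differential dilution of a secondary outcome and of exploratory odds ratios. It is largest for Step 3, small for the ten-step count, and for Step 6 at Day 180 limited mainly to people who stop MOUD or miss later visits. The primary ORBC outcome is untouched.

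The date arithmetic rests only on the documents. The size of the dilution rests on assumed rates and on independence of earlier and later contacts; if people with earlier contacts also tend to have later ones, it is smaller. It would also be wrong to say that the look-back at this visit always lies mostly before randomization: that is true through Day 44, exactly half at Day 45, and false on Days 46 to 51.

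**What to change.** Amend SAP 7.4.1 and the matching text in Protocol 7.2.1:

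- **Step 6:** credit only from the Day 90 visit onward. The overlap is then at most 14 days, at a visit on Day 76, when 76 days since randomization are already available against the 70 required.
- **Step 3:** count only contacts after Day 0, so that credit at Day 30 means three contacts since randomization. State how contacts on Day 0 itself are treated, because a TAU peer session before randomization and the first PILOT contact can fall on the same day.
- **Fallback for Step 3:** if the form cannot separate earlier from later contacts, credit the step from the Day 90 visit and add a sensitivity analysis using the baseline Step 2-7 form, which is already collected.

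If the form already withholds the 90-day items at Day 30, the amendment simply records that rule.

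The cost is about one sentence per step, with no new data collection under the Step 6 change or the Step 3 fallback. A few Day 30 credits are lost. Under the fallback these include some genuine Step 3 credits in people who later drop out, because SAP 7.4.1 treats missing data as a step not met. People who continue prior MOUD can still earn the other MOUD steps; this change does not address that.

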8. **Decrease SUD Severity**: A participant will achieve Step 8 if the number of current SUD criteria met on the DSM-5 Checklist for the primary SUD decreases as compared with baseline at the 30-, 60- OR 180-day visit. A participant will be counted as having met Step 8 if the number of criteria decreases below the baseline score at ANY study visit, even if there is/was an increase in number of DSM-5 criterion met at previous or subsequent study visits.
9. **Early Remission**: A participant will have achieved Step 9 if the participant met 2 or more SUD criteria for any substance at baseline and subsequently meets 0-1 current SUD criteria for that substance on the DSM-5 Checklist AND has a toxicology screen negative for that substance at 30-day and 90-day OR 90-day and 180-day study visit. If a participant meets criteria for more than one SUD, the participant will have met criteria for Step 9 even if remission is not achieved in each SUD identified.
10. **Increase in Recovery Capital Score**: A participant will have achieved Step 10 if the total score on the Assessment of Recovery Capital (ARC) scale [34] (range 0-50) increases by a value equivalent to 0.5 standard deviations within the validation sample, which was 11.54 [22] (5.77 point increase or greater needed to meet Step 10), from baseline to the 30- 90- OR 180-day visit. A participant will be counted as having met Step 10 if they increase above the baseline score at ANY study visit even if there is/was a decrease in ARC at previous or subsequent study visits.

If the algorithm is unclear regarding whether a specific step was achieved post-randomization, it will be adjudicated by an independent committee at the end of the trial.

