10. Increase in Recovery Capital Score: A participant will have achieved Step 10 if the total score on the Assessment of Recovery Capital (ARC form) scale (Groshkova, et al.; range 0-50) increases by a value equivalent to 0.5 standard deviations within the validation sample score of 11.54 (Ward, et al.) from baseline to the 30- 90- OR 180-day visit. This equates to a 5.77 or greater point increase. A response of “agree” counts as one point. A participant will be counted as having met Step 10 if they increase above the baseline score at ANY study visit even if there is/was a decrease in ARC at previous or subsequent study visits.

If the algorithm is unclear regarding whether a specific step was achieved post-randomization, it will be adjudicated by an independent committee at the end of the trial. Should it be unclear if a specific step was achieved, the following dispute resolution will be employed. A Dispute Resolution Panel will be formed that includes 3 members. One member will be selected by the NIDA CCTN, one member will be selected by the lead team, and those two members will select a third that is independent and a context expert in opioid-related overdose. That 3-member committee will then be asked to determine if the step is met based on the definition above.

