## 7.7 Definition of the Exploratory Outcome Measures

1. Exploratory Aim 1: To assess the effects of PILOT versus TAU on the achievement (yes/no) and magnitude of achievement (e.g., improvement in Addiction Recovery Capital Scale by 3 points, number of steps achieved) on the modified SUD Cascade of Care.
2. Exploratory Aim 2: To evaluate the effectiveness of PILOT versus TAU on initiation of MOUD in the ED (EDM) for those with any level of OUD at baseline (DSM; assessed via self-report upon ED discharge or in follow-up assessment if unable to be assessed at ED discharge).
3. Exploratory Aim 3: To assess the effects of PILOT versus TAU on substance use frequency at 30, 90, and 180 days via self-reported days of illicit opioid use measured by Timeline Follow-Back (TLFB).
4. Exploratory Aim 4: To evaluate the degree of engagement in Peer Support Services in those randomized to PILOT versus TAU at 30, 90, and 180 days, measured as the number of contacts received or initiated with a Peer Support Specialist in the past month (PIL; phone, video, or in-person).

5. Exploratory Aim 5: To evaluate the effectiveness of PILOT versus TAU on self-reported attendance in 12-step meetings, peer support services, other recognized recovery organization, or formal SUD treatment at any time point during enrollment, defined as self-report of having attended a meeting or appointment (SAA; phone, video, or in-person).
6. Exploratory Aim 6: To evaluate the effectiveness of PILOT versus TAU on the percentage of urine toxicology screens (UDT) positive for primary substance of use (as per DSM-5 Checklist: opioids, alcohol, amphetamines, cannabis, cocaine, or sedatives) at 30-, 90-, 180-, and 210-days post-randomization.
7. Exploratory Aim 7: To evaluate the effectiveness of PILOT versus TAU on repeat non-fatal overdose (ODI) and 210-day rates of death (DTH; all-cause mortality), including death by overdose.

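### Step 10 sets a 5.77-point threshold, but its closing sentence, read literally, counts any rise above baseline; the sentence should be tied to the threshold in both documents

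*SAP*

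**What the plan says.** SAP 7.4.1 says Step 10 is achieved if the total score on the Assessment of Recovery Capital (ARC) "increases by a value equivalent to 0.5 standard deviations within the validation sample score of 11.54", measured "from baseline to the 30- 90- OR 180-day visit". It then gives the figure: "This equates to a 5.77 or greater point increase". The score runs from 0 to 50, and each item answered with agreement "counts as one point", so totals are whole numbers. Protocol 7.2.1 has the same rule and is firmer about it: "5.77 point increase or greater needed to meet Step 10".

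The closing sentence, identical on this point in the two documents, reads: "A participant will be counted as having met Step 10 if they increase above the baseline score at ANY study visit". It goes on to say that a fall at another visit does not matter. It names no minimum rise and does not refer back to the threshold.

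Both documents send unclear step determinations to an independent committee at the end of the trial. The SAP adds that this three-member panel decides on the basis of the definition just given.

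**The concern.** A programmer who codes the threshold and one who codes the closing sentence will classify some participants differently, and neither document says which governs. The Protocol cannot be used to correct the SAP, because it contains the same pair of sentences.

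Step 10 adds one to a count from 0 to 10 that SAP 7.5.1 tests at a two-sided 5% level. It is also reported separately in SAP Table 35 and modelled as a binary outcome in SAP 7.8. If the looser sentence were applied, part of the count would reflect ordinary fluctuation in a questionnaire score. The trial is open-label, so the criterion should not be left to a choice made at the end of the trial, when outcome data exist.

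**Working it through.** **Reproducing the threshold.** 0.5 × 11.54 = 5.77, as stated. On a whole-number score the smallest qualifying rise is 6.

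**Where the two sentences differ.**

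| Best rise over baseline | Threshold | Closing sentence |
|---|---|---|
| 0 or less | not met | not met |
| 1 to 5 points | not met | met |
| 6 points or more | met | met |

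**Comparison with the other steps.** In Steps 1 to 6 the corresponding sentence points back to the criteria already stated, so it only adds persistence. Step 8 is worded like Step 10, but any decrease in the number of criteria is itself the Step 8 rule, so nothing conflicts. Steps 7 and 9 have no such sentence. Step 10 is the only step whose counting sentence departs from its own threshold.

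**Chance attainment with no true change.** If baseline and k follow-up scores are exchangeable (a stable true score plus independent error), baseline is the highest of the k + 1 readings with probability 1/(k + 1) for a continuous score. The chance that at least one follow-up exceeds baseline is therefore k/(k + 1), whatever the reliability. For Days 30, 90 and 180, k = 3 gives 3/4 = 75%. If Day 210 also counted, k = 4 gives 4/5 = 80%. Ties and the limits of the scale lower these figures.

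A simulation allowed for ties and limits, with 400,000 participants per setting, scores rounded and held to 0–50, and three follow-up visits. From the documents: SD 11.54 (the validation sample), the range, the whole-number unit, the visits, and missing data counted as not met. Assumed, because the documents do not give them: retest reliability 0.5 to 0.95, mean 25 to 40, independent attendance of 60 to 100% per visit, and a baseline score for everyone.

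| Mean | Reliability | Attendance | Any rise | 5.77 or more | Gap (points) |
|---|---|---|---|---|---|
| 25 | 0.5 | 100% | 73.0% | 54.5% | 18.5 |
| 25 | 0.8 | 100% | 71.6% | 41.7% | 29.9 |
| 25 | 0.95 | 100% | 68.2% | 14.6% | 53.6 |
| 35 | 0.8 | 100% | 67.4% | 37.9% | 29.5 |
| 40 | 0.8 | 100% | 61.4% | 33.2% | 28.2 |
| 40 | 0.95 | 100% | 57.4% | 11.5% | 45.9 |
| 25 | 0.5 | 60% | 57.5% | 40.6% | 16.9 |
| 40 | 0.95 | 60% | 44.9% | 7.7% | 37.2 |

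Over all settings, any rise ranges from 45 to 73%: 57–73% with full attendance, 52–67% at 80% per visit, and 45–58% at 60%. The 5.77-point rule ranges from 8 to 55%.

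**Effect on the step count.** At reliability 0.8 and full attendance the looser sentence adds 0.28 to 0.30 of a step per participant. As an illustration with assumed arm means (the documents give none), adding 0.3 to both arms changes 5 against 4 steps from a ratio of 1.25 to 5.3/4.3 = 1.23, and 3 against 2 steps from 1.50 to 3.3/2.3 = 1.43.

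**The case against.** The strongest reply is that there is only one threshold. The Protocol makes 5.77 points necessary, the SAP repeats the figure, and the closing sentence contains no number. Similar sentences elsewhere in the cascade express persistence, and this one closely follows Step 8, so it looks like carried-over wording. As an account of intent this is the likelier reading, and it stands. It does not remove the defect, because the sentence states a condition for counting the step that is not the threshold. The general eligibility rule already provides persistence at any visit, so nothing is lost by correcting it.

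A second reply is that adjudication would catch the problem. It is weak protection, because the panel must apply the same conflicting definition.

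A third is that the harm is small. Much of this stands. The 5.77-point rule, taken as the best of three visits, is itself often met by chance, so only the gap is due to the wording. With equal attendance the excess falls on both arms and attenuates the ratio modestly.

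A reader might also infer a third Step 10 threshold from Exploratory Aim 1, which mentions "improvement in Addiction Recovery Capital Scale by 3 points". The documents do not support that. The figure is offered as an example of magnitude, listed apart from yes/no achievement, and the analysis planned for that aim treats each step as binary.

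**Conclusion.** The inconsistency is real and is present in both documents. Taken literally, the closing sentence credits rises of 1 to 5 points that the threshold excludes, and so changes a count tested as a secondary outcome.

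Its size is conditional. With no true change and SD 11.54, roughly 45 to 75% of participants would meet the looser sentence by chance, against roughly 10 to 55% for the threshold, depending on reliability, mean and attendance. At reliability 0.8 with full attendance the gap is about 30 percentage points. It would be tempting to say that about two thirds of unchanged participants would be credited. That figure fits central settings with near-complete attendance, but the documents give no reliability, expected mean or attendance, so it cannot be stated as a property of the plan.

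Nor do the documents show that the treatment comparison would be biased. With equal attendance the main effect is dilution. Unequal attendance could turn chance attainment into bias, because missing data count as not met, but nothing in the plan says attendance will differ. The primary analysis of overdose risk behaviors is unaffected. The correction should be made because it is nearly free and settles the criterion in advance.

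**What to change.** Replace the closing sentence of Step 10 in Protocol 7.2.1 and SAP 7.4.1 with wording such as: *A participant meets Step 10 when the ARC total at Day 30, Day 90 or Day 180 is at least 5.77 points (in practice 6, as the score is in whole numbers) higher than at baseline; a lower score at an earlier or later visit does not cancel the step.*

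Naming the visits also settles whether Day 210 can count. The battery is given then too ("At Day 30, Day 90, Day 180, and Day 210 visits, participants will be asked"), and the present reference to any study visit leaves that open.

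The cost is one sentence in each document, with no change to data collection, visits or the model. It should be done before steps are tabulated by arm. It will not remove chance attainment under the 5.77-point rule, but it ensures that the threshold analysed is the one the plan sets out.
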